#### Sub-study

Semi-structured interviews: 32 participants will be invited to take part in one semi-structured interview with a trained interviewer. The highly selected nature of the sample, and the topic sensitivity, mean that decision-making and experiences of termination will be their indirect rather than direct focus. Interviews will be of up to 90 minutes duration and will be divided into two discrete sections.

In part 1 women will be asked about general issues connected with their experience of entering and participating in the trial, and their understanding of its design and methods. This part of the interview will indirectly elicit accounts of their experience of referral pathways into the service and trial, specific accounts of their experiences of termination, and its outcome.

In part 2 the interviewer will describe and demonstrate outcomes of a conjoint analysis (refer to section 15) using structured questions and flashcards. Subjects will be invited to comment on the model derived from conjoint analysis from the perspective of a 'notional other' [31], and will also be asked about the 'fit' between the 'willingness to pay' model and their own experiences.

With the consent of the participant, each interview will be audio-recorded using an unobtrusive mini-disk recorder and conference microphone, and later transcribed. Where participants do not consent to recording, handwritten notes will be made.

# 14.2 Data handling

Study data collected will be entered directly, where possible, to avoid transcription errors, into a web-based PowerTrial data capture system by the research nurse, or participant for the web-based questionnaires. The remaining study data will be entered from paper source. Audit trail and full daily back-up will be provided.

Data will be collected to standards required by CFR Title 21, part 11, and EU Directive

2001/20/EC, and adhere to the Data Protection Act 1998.

The quality and retention of study data will be the responsibility of the Newcastle Clinical Trials Unit. All study data will be archived in line with Trust policy (currently 10 years).

## **15** STATISTICAL CONSIDERATIONS

# **15.1 Statistical analysis**

The analysis strategy will be similar to that used in a partially randomised preference trial of treatment for depression [43]. The trial will contain 4 intervention groups:

- 1 randomised to medical termination (RM)
- 2 randomised to surgical termination (RS)
- 3 preference for medical termination (PM)
- 4 preference for surgical termination (PS)

The analysis will be on an intention to treat basis (although it is anticipated that women will always get the randomised or preferred intervention). Those in either medical arm (RM or PM) who subsequently receive surgical intervention, due to incomplete or missed abortion, will be analysed as per the assigned medical arm.

Baseline variables - Although randomisation should balance out baseline characteristics, it will be important to compare these in the four groups to see if those who are prepared to be randomised differ from those who have a preference. If so, there are problems in extrapolating any conclusions from the randomised arms to the general population.

### Primary analysis

Main comparison of randomised arms:

- a. Comparison of proportions of women finding the procedure acceptable. We will also investigate the interaction between past history of TOP and intervention group on acceptability and gestational age (as a continuous variable) and intervention group on acceptability
- b. Comparison of mean values on psychological and rating scales.
- c. Comparison of proportions of women rating care as 'excellent'
- d. Comparison of WTP between those women in the two randomised groups.

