# **13 RANDOMISATION**

Participants with a procedure preference will decide whether to opt for a medical or surgical termination.

Participants with no preference, and willing to be allocated a procedure at random, will be randomised using a computer system with web-based access for trial personnel (PowerTrial). Randomisation will be stratified according to gestation (less than 9 weeks and between 9 & 13 weeks) and for previous termination of pregnancy.

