#### Secondary analysis

Secondary comparison of medical and surgical arms (preference and randomised subgroups combined):

- a. Comparison of proportions of women finding the procedure acceptable and rating the quality of care as 'excellent' the comparison will adjust for key baseline variables using logistic regression. We will also investigate the interaction between past history of TOP and intervention group on acceptability, and gestational age (as a continuous variable) and intervention group on acceptability.
- b. Comparison of mean values of psychological and rating scales the comparison will adjust for key baseline variables using multiple regression.
- c. Comparison of proportions of women with emergency admission and particular symptoms the comparison will adjust for key baseline variables using logistic regression.
- d. Comparison of WTP between those women in the combined groups.

Tertiary comparison of combined preference and randomised groups:

The aim of this comparison is to determine if receiving a preferred intervention improves key outcomes. Comparisons will be of acceptability, psychological and rating scales with methods as for secondary comparisons.

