# **15.2 Sample size calculation**

The power of the study is based on the main comparison of acceptability between women randomised to medical or surgical TOP. Assuming the acceptability of medical termination to be 75%, we would need responses from 335 women in each randomised arm to detect a difference in acceptability of 10% (i.e. from 75% to 85%) with a significance level of 5% and power of 90%. We believe this difference in the level of acceptability is important for both consumers and providers; a similar difference was employed by Ashok et al [15] in their large randomised comparison of abortion methods.

Based on the power calculation we need primary outcome data on 670 women randomised to medical or surgical TOP at <14 weeks' gestation. In order to achieve this number we calculated;

- 1. 1116 women need to be randomised (assuming 40% of women randomised fail to attend for follow up and primary outcome data is therefore not available).
- 2. 2232 women need to be recruited (assuming 50% of women agreeing to participate in the study have a preference for medical or surgical TOP and are therefore not suitable for randomisation).
- 3. 3188 women need to be approached (assuming 30% of women accepted for TOP will decline involvement in the study).

Justification for assumptions – All three assumptions were based on our experience from an earlier pilot trial conducted at the RVI involving women requesting TOP at 9-13 weeks' gestation. For reasons detailed in [25] we believe our assumption of 60% follow up is conservative. Further, previous trials conducted in the UK have reported that 54% [14] and 82% [15] of recruited women undergoing TOP at < 9 weeks and 9-13 weeks respectively were prepared to have their method of TOP determined by randomisation. Thus our estimate of 50%

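### The main randomised comparison names no adjustment for the two stratification factors: valid, but slightly conservative, and free to improve

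*Protocol*

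**What the plan says.** - Protocol section 13 (Randomisation): "Randomisation will be stratified according to gestation (less than 9 weeks and between 9 & 13 weeks) and for previous termination of pregnancy". Two binary factors give four strata.
- Protocol section 15.1, Primary analysis, item a: "Comparison of proportions of women finding the procedure acceptable". The same item goes on to plan interactions of intervention group with past termination and with gestational age taken as continuous. It names no test, model or adjustment for the main effect.
- Items b to d of that list are equally brief. Item b reads "Comparison of mean values on psychological and rating scales"; items c and d compare excellent ratings and willingness to pay. None mentions the stratification factors.
- Section 15.1, Secondary analysis, takes the same acceptability endpoint in the combined medical and surgical arms and says "the comparison will adjust for key baseline variables using logistic regression". Multiple or logistic regression is also stated for the scales, emergency admission and symptoms; the willingness-to-pay item names no adjustment. The adjusting variables are not listed.
- Section 15.2: "we would need responses from 335 women in each randomised arm", for 75% against 85% at 5% significance and 90% power.

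**The concern.** When randomisation is stratified on factors that predict the outcome, the arms are balanced on those factors by design, and the difference between arms varies less than a simple two-sample formula supposes. An analysis that leaves the factors out uses too large a standard error, so its interval is somewhat too wide and its p-value somewhat too large.

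The protocol has reasons to think the factors may matter. Section 7 says acceptability may be lower at later gestations, and names gestational age and prior experience among possible reasons for the spread in preference rates. Section 15.1 picks both factors for interaction tests. An interaction test asks whether the effect differs between subgroups; it does not supply an adjusted overall effect with an interval that reflects the design.

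The wording also reads as a choice and not only as brevity. Adjacent lists treat the same endpoint, and adjustment is written into one and absent from the other. At stake is a little precision on the primary endpoint, and a choice between crude and adjusted results left open until the data are seen.

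**Working it through.** **Step 1. Reproduce the plan's figure.** Inputs from section 15.2: 75% and 85%, alpha 5% (two-sided assumed; the protocol does not say), power 90%. Two-proportion formula with pooled variance under the null and no continuity correction:

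n per arm = [1.960 × √(2 × 0.80 × 0.20) + 1.282 × √(0.75 × 0.25 + 0.85 × 0.15)]² / 0.10²
= (1.1087 + 0.7193)² / 0.01 = 334.2, rounded up to **335**.

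This matches the stated figure; power at 335 is 90.1%. The unpooled formula gives 331 and the continuity-corrected one 354. The trial is therefore sized on a crude comparison.

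**Step 2. Why the crude test is conservative.** Let R² be the share of outcome variance explained by the strata. With balance within strata, the true variance of the difference is about (1 − R²) times the variance the crude test uses. Its actual type I error is then about 2 × [1 − Φ(1.96 / √(1 − R²))], which is at most 5%.

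The protocol gives neither stratum shares nor stratum-specific acceptability, so the following are assumptions: 45% at 9 to 13 weeks, 30% with previous termination, overall acceptability 80%.

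R² = [0.45 × 0.55 × dg² + 0.30 × 0.70 × dt²] / (0.80 × 0.20), where dg and dt are the acceptability gaps by gestation and by previous termination.

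| dg, dt (points) | R² | 670 / (1 − R²) − 670 | Approximate crude type I error |
|---|---|---|---|
| 10, 5 | 1.9% | +13 | 4.8% |
| 15, 10 | 4.8% | +34 | 4.5% |
| 20, 15 | 9.1% | +67 | 4.0% |

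The third column is the gain from adjustment expressed as equivalent extra responders on the planned 670.

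**Step 3. Simulation of type I error and power.** 335 per arm, 20,000 replicates, exact balance within four strata. Assumed shares here: 40% at 9 to 13 weeks and 30% with previous termination, so about 141, 60, 94 and 40 women per arm in the strata. Marginal acceptability is 80% in both arms under the null, and 75% against 85% under the alternative. The crude two-proportion z-test is set against the stratified Mantel-Haenszel (CMH) test. Odds ratios are for later gestation and previous termination respectively.

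| Assumed odds ratios | Type I, crude | Type I, stratified | Power, crude | Power, stratified |
|---|---|---|---|---|
| 1, 1 (none) | 5.1% | 5.0% | 90.0% | 89.9% |
| 0.6, 0.7 (moderate) | 4.8% | 5.0% | 90.6% | 90.8% |
| 0.4, 0.5 (strong) | 4.4% | 4.9% | 91.4% | 92.0% |
| 0.25, 0.35 (very strong) | 3.7% | 4.7% | 91.6% | 93.2% |

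Simulation error is about √(0.05 × 0.95 / 20,000) = 0.15 points for type I error and √(0.90 × 0.10 / 20,000) = 0.21 points for power. The power difference runs from nil to 93.2 − 91.6 = 1.6 points. The last row is an extreme case: medical-arm acceptability runs from 89.3% in the best stratum to 42.3% in the worst, a gap of 47.0 points. In the moderate row the range is 80.7% to 63.7%, a gap of 17.0 points.

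The approximation in step 2 and the simulation agree in direction and size.

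**The case against.** The strongest reply is that silence is not a decision. A Mantel-Haenszel difference is also a comparison of proportions, the text never says unadjusted, and the statistical analysis plan, which was not available, may settle it. The contrast with the secondary list has an innocent explanation too: the combined arms include self-selected women, so confounding must be dealt with there, while section 15.1 expects randomisation to balance baseline characteristics. This part stands: the protocol does not prescribe a crude analysis in so many words. It still reads as one, given the adjacent adjusted list and a sample size that follows exactly from the crude formula.

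Three stronger readings are tempting, and the document does not support them.

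- *That the primary analysis ignores the strata.* For acceptability it does not: the interaction work in item a uses both factors, and a conventional interaction model contains their main effects. Only items b to d leave them out altogether.
- *That the primary p-value or interval is invalid.* Step 3 shows no inflation of type I error. Any discrepancy is on the safe side, and crude power stays at about 90% or above.
- *That the planned 40% loss makes adjustment necessary to avoid bias.* Section 7 reports lower pilot follow-up in the surgical arm (95% interval for the difference 2% to 31%), so imbalance among responders is plausible. But the protocol gives no follow-up rate by gestation or previous termination, so no size can be put on it. Such imbalance would also weaken the conservatism argument, which rests on balance within strata.

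The upper values in the working are generous. For previous termination the protocol gives no acceptability figures. For gestation, the figures in section 7 overlap: 63 to 92% before 9 weeks, and 79% and 70% at 10 to 13 weeks, the latter with response below 50%.

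**Conclusion.** The point holds as a modest improvement, not as a validity error. The main randomised comparison names no adjustment of the treatment effect for the factors used to randomise, while most combined-arm comparisons are adjusted. If the strata carry no prognostic information, nothing is lost. If they do, the crude test is conservative by up to about 1.3 points of type I error (5% nominal against 3.7%) and gives up at most about 1.6 points of power, both in the most extreme case tried.

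These sizes rest on assumed stratum shares and effects, exact balance within strata and a two-sided 5% test. The direction does not depend on the particular values, provided the arms remain balanced on the strata among responders.

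**What to change.** In section 15.1, Primary analysis, replace item a's first sentence with wording such as: *The difference between the randomised medical and randomised surgical arms in the proportion finding the procedure acceptable will be estimated with a 95% confidence interval, adjusted for gestation stratum (under 9 weeks, 9 to 13 weeks) and previous termination, by the Mantel-Haenszel risk difference or by logistic regression with a standardised risk difference. The unadjusted difference will be reported as supportive.*

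Either method keeps the result on the scale of the 10-point difference on which the trial is sized; choose one in advance. Add that items b to d are adjusted for the same two factors, with linear regression for the scale means. The interaction analyses can stay as they are. If the statistical analysis plan already says this, the protocol need only agree with it.

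The cost is wording only. Both factors are needed to randomise, so they are known for every randomised woman, and 335 responders per arm remains sufficient.

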Service users' evaluations of the care they have received are clearly important in the context of current initiatives to develop a more patient-centred NHS. Patient satisfaction with their care is the most commonly used indicator in research on patient evaluations [19], but definitions of satisfaction vary, and different measures incorporate different dimensions of the construct, such as adequacy, suitability and acceptability. A common problem with satisfaction measures is that they exhibit ceiling effects i.e. most patients report being satisfied, and distinctions between care of different quality are often not observed. This is likely to be a particular problem in areas such as termination of pregnancy, where patients are widely observed to experience a sense of relief after the procedure. Most studies of women's views about termination of pregnancy have reported procedure acceptability; typically women have been asked whether they would opt for the same method in the future or recommend the method to a friend [13, 17, 20]; data from randomised trials indicate that acceptability of both methods before 9 weeks gestation is high (63-92%) with 2-36% of women randomised to surgical termination of pregnancy preferring a medical procedure in future and 22-37% of women randomised to medical termination of pregnancy preferring a surgical termination of pregnancy [13, 15]. Where women have a preference for one method, typically  $\geq 90\%$  would choose the same method in the future [14, 16-18, 20]. Acceptability may be lower at later gestations; in the only randomised trial of abortion methods between 10-13 weeks, more women opted for VA again than medical abortion (79% vs. 70% respectively) [15]. However response rates were low (<50%). The results reported above are based on the 'single question with a binary outcome' approach to assessing acceptability. Such measures are simple to collect and report but provide limited information, particularly about why respondents hold the views they do. One supplementary approach is to ask respondents to rate specific features of their care thereby providing information about the reasons underlying acceptability judgements. Using a semantic differential rating scale, Henshaw et al. [14] identified that in randomised women, medical abortion rated lower on 6 of the bipolar adjectives with pain showing by far the largest difference. Vacuum aspiration was also rated less painful in women allocated according to preference.

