Strength of preference - To measure women's strength of preference for medical or surgical termination we will measure willingness to pay. This technique is being increasingly used in health technology assessment [32] and has been used previously for assessing strength of preference for abortion method [23, 33]. Interviews will be conducted, using the payment card method [34], in all women in the preference arm prior to the procedure where they will be asked to state their maximum 'willingness to pay' amount for the termination method they have chosen. Interviews will also be conducted on all women in both the randomised and preference arms at 2 weeks after the procedure when they will be asked to state their maximum 'willingness to pay' amount to receive their preferred option at a future date. The validity of women's responses will be tested by examining the correlation between stated 'willingness to pay' and level of income.

Satisfaction with care - The methodological pitfalls of measuring satisfaction with care have been reviewed recently [35]. Women will be asked to rate the quality of care during the termination and the counselling and support afterwards using a 5 point Likert scale (from excellent to poor) at 2 weeks and 3 months after the procedure. Measures in which patients are asked to rate the quality of aspects of their care show greater response variability than measures which seek direct ratings of satisfaction [36] and are better predictors of whether patients will return to the same doctor in the future [36]. For analysis we will distinguish those who rate their care as excellent from the remainder as this provides better discrimination [37]. A similar assessment has been used in our pilot trial. Ratings of care will be supplemented by information on satisfaction with care from the qualitative study.

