# Appendix B: Willingness to Pay

### **Methods and Questions**

Women will be asked to state their WTP for their preferred method of termination at the following points

1. Pre TOP – for women expressing a preference and enrolled in the 'preference arm' we will ascertain the maximum amount WTP using the payment card method

2. Post TOP – all women who underwent TOP will be asked which method they would choose if undergoing a future TOP and IF they would be WTP an amount to receive that preferred option at a future date. If they answer 'yes' to this we will ascertain the maximum amount WTP using the payment card method

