### **Payment Card Method**

The concept of willingness to pay and the payment card method have been used previously in a study of women's preferences in the termination of pregnancy [52].

In this study once respondents have indicated if they have a preference for a particular method of termination and that they would be willing to pay to access that method they will be handed a card containing a list of values from £0 to £1000 and £1000 plus. £0 £60 £140 £300 £800£5 £70 £160 £350 £900£10 £80 £180 £400 £1000£20 £90 £200 £450 £1000+£30 £100 £225 £500£40 £110 £250 £600£50 £120 £275 £700 £1000 If £1000+, can you say what is the exact amount?

Respondents will be asked to put a cross by the amounts that they would definitely not pay and then to consider what would be the maximum amount that they would be willing to pay by circling the relevant value. If respondents indicate '£1000 plus' they will asked to write in the amount. All respondents will be asked an open ended question regarding why they chose the amount indicated.

Other data to be collected:

Income, age, age at which left education, occupation, previous operation with a general anaesthetic (yes/no)

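### Both WTP comparisons ignore which method each woman is valuing, so on their own they show intensity of preference, not strength of preference for medical versus surgical

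*Protocol*

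**What the plan says.** Section 14.1 gives the purpose: to capture "strength of preference for medical or surgical termination we will measure willingness to pay". Strength of preference is a secondary objective (section 8) and a secondary outcome (section 9).

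At 2 weeks women in both the randomised and preference arms state the most they would pay, as an "amount to receive their preferred option at a future date". Appendix B gives the order of questions: "all women who underwent TOP will be asked which method they would choose if undergoing a future TOP and" whether they would pay for that method. Those who would pay then use a payment card: "they will be handed a card containing a list of values from £0 to £1000 and £1000 plus". Women unwilling to pay are asked why, and Appendix B notes that protest zeros must be told apart from women with no demand.

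Section 15.1 lists, as item d of the primary analysis, "Comparison of WTP between those women in the two randomised groups", and as item d of the secondary analysis, "Comparison of WTP between those women in the combined groups". Neither says which method the amount is for.

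The protocol expects preferences to be mixed within a randomised arm. Section 7 cites trials with "22-37% of women randomised to medical termination of pregnancy preferring a surgical termination of pregnancy", and 2-36% of women randomised to surgical preferring medical. Section 15.2 plans on acceptability of 75% and 85%.

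**The concern.** The item being valued is not fixed by arm. In the randomised medical arm (RM), a woman who would pay £300 for medical again and a woman who would pay £300 for surgical next time add the same £300, because the card has no negative values. The same holds in the randomised surgical arm (RS).

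A higher figure in one arm may therefore mean that women strongly want that method again, or that a minority strongly want to avoid it. Those readings have opposite implications for providers, and item d alone cannot separate them. At stake is the interpretation of a named secondary outcome, not the primary outcome.

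**Working it through.** **Inputs.** Planning acceptability is aM = 0.75 in RM and aS = 0.85 in RS (section 15.2). The protocol gives no WTP amount, spread or target difference, so all pound amounts below are assumptions. Item d names no summary statistic; means are used here. A woman who would not opt for the same method is treated as preferring the other.

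**1. The plan's own figure.** With two-sided 5% significance, 90% power, pooled variance and no continuity correction:

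n = [1.960 x sqrt(2 x 0.80 x 0.20) + 1.282 x sqrt(0.75 x 0.25 + 0.85 x 0.15)]^2 / 0.10^2 = 334.2, rounded up to 335 per arm, as stated. The point below does not depend on this figure; it only uses the same 75% and 85%.

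**2. Share valuing the other method.** RM: 1 - 0.75 = 25%. RS: 1 - 0.85 = 15%. With the cited 22-37% for women randomised to medical, the range is about 15-37%. The cited range for women randomised to surgical starts lower, at 2%.

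**3. Unsigned against signed amounts.** Let WM and WS be the mean amounts offered for medical and surgical.

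- Unsigned: RM = aM x WM + (1 - aM) x WS; RS = aS x WS + (1 - aS) x WM.
- Signed relative to the allocated method (plus if for the same method, minus if for the other): RM = aM x WM - (1 - aM) x WS; RS = aS x WS - (1 - aS) x WM.

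With £100 throughout, unsigned RM = 75 + 25 = 100 and RS = 85 + 15 = 100. Signed RM = 75 - 25 = +50 and RS = 85 - 15 = +70.

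| Assumed WM / WS (£) | Unsigned RM, RS (RM - RS) | Signed to allocated method RM, RS (RM - RS) |
|---|---|---|
| 100 / 100 | 100, 100 (0) | +50, +70 (-20) |
| 100 / 200 | 125, 185 (-60) | +25, +155 (-130) |
| 200 / 100 | 175, 115 (+60) | +125, +55 (+70) |
| 50 / 300 | 112.5, 262.5 (-150) | -37.5, +247.5 (-285) |

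From the first row to the last, the unsigned RM figure rises from £100 to £112.50 while the signed figure falls from +£50 to -£37.50. In the last row, 0.25 x 300 = £75 of the £112.50 is offered for surgical, by women who had been allocated medical.

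**4. Does reporting acceptability beside it resolve this?** Hold RM acceptability at 75%.

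- Amounts of £50 (medical) and £250 (surgical): unsigned 37.5 + 62.5 = £100; signed 37.5 - 62.5 = -£25.
- Amounts of £120 and £40: unsigned 90 + 10 = £100; signed 90 - 10 = +£80.

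Acceptability and unsigned WTP are identical, but net strength of preference has opposite signs.

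**5. Choice of sign.** Coding medical as plus and surgical as minus, with equal amounts W, gives RM - RS = W(2aM - 1) - W(1 - 2aS) = 2W(aM + aS - 1). At W = £100 this is £120 for aM/aS of 75/85, 80/80 and 85/75 alike. Signing relative to the allocated method gives 2W(aM - aS): -£20, £0 and +£20. Only the second responds to which method is more acceptable.

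**6. Combined arms.** Section 7 says that typically at least 90% of women with a preference would choose the same method again, so at most about 10% value the other. With half of participants having a preference (section 15.2), and assuming an even split between methods and equal follow-up, the shares valuing the other method are at most about (25 + 10)/2 = 17.5% in medical and (15 + 10)/2 = 12.5% in surgical.

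**The case against.** The case on the other side has real force.

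- **Item d does not specify an unsigned mean.** True: coding and summary statistic are often left to a statistical analysis plan, and one not shown could define a signed or stratified measure. But the protocol itself fixes what each woman values, a card without direction, and a plain between-arm contrast. Those do not fit the stated purpose.
- **Direction is already the primary outcome, and the protocol plans to explore how WTP, satisfaction and acceptability relate.** This would come close to WTP by preferred method. It is exploratory, however, and does not change the contrast in either item d. Step 4 shows that acceptability and WTP reported separately do not suffice.
- **The unsigned comparison has a meaning.** It does: whether allocation changes the amount attached to a woman's own preferred option. A reader might infer that item d is meaningless or cannot inform strength of preference at all. The documents do not support that; it measures intensity.
- **The £100 example has equal intensity by construction.** True, so an unsigned difference of zero is the right answer about intensity. A reader might also infer that the plan misses a £120 difference between RM and RS. Step 5 shows why that figure is no evidence: it mainly reflects women preferring the method they had.
- **The combined comparison is less exposed.** This stands (step 6).

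**Conclusion.** The point holds in a limited form. As written, both items d compare amounts without regard to the method valued, and so show intensity but not, on their own, strength of preference for medical versus surgical. The problem is clearest in the randomised arms, where about 15-37% are expected to prefer the other method, and smaller in the combined arms.

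At planning acceptability and an assumed £100 throughout, unsigned figures of £100 and £100 correspond to +£50 and +£70 when signed relative to the allocated method. The size depends wholly on amounts the protocol does not give: across the assumed amounts the unsigned RM - RS difference ran from -£150 to +£60 and the signed one from -£285 to +£70. It also rests on treating a negative answer on acceptability as preferring the other method. The primary outcome, the sample size and the data to be collected are unaffected.

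**What to change.** In both items d of section 15.1:

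1. Report 2-week WTP by preferred future method within each arm, beside the share preferring each method.
2. For the between-arm comparison, sign the amount relative to the allocated method (the chosen method in the preference groups): positive if for the same method, negative if for the other, zero for genuine non-demand. Set protest zeros aside, using the distinction Appendix B already foresees, and report their number by arm.
3. Do not use the RM - RS difference in amounts coded medical plus, surgical minus as the measure.
4. If the unsigned comparison is kept, label it as intensity of preference only.

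The cost is a change of wording. Appendix B already has each woman "asked which method they would choose if undergoing a future TOP" before the amount is elicited, so no new data are needed.
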